2. STUDY OBJECTIVE

2.1 Primary Objective

The primary objective is to evaluate the efficacy of Racecadotril in addition to standard treatment oral rehydration solution (ORS) in infants and children (3 months until 60 months) with acute diarrhea measured as duration of diarrhea (hours) between the start of treatment until final diarrheal/watery stool or end of study treatment (treatment duration maximal 5 days).

Duration of diarrhea is defined as date and time of the evacuation of the final watery/diarrheal stool derived from the daily diary.

2.2 Secondary Objective(s)

- Time until recovery, defined as date and time of the evacuation of the first of two consecutive normal stools or no stool within 12 hours after the first normal stool.
- Number of recovered subjects in total and until each individual treatment day. Mean and median time until recovery.
- Global Physician Assessment (GPA) at the end of treatment (at the discretion of the investigator):
 - \circ 1 = Complete relief of acute diarrhea,
 - \circ 2 = marked improvement of acute diarrhea,
 - \circ 3 = moderate improvement of acute diarrhea,
 - \circ 4 = slight improvement of acute diarrhea,
 - \circ 5 = no change in acute diarrhea,
 - \circ 6 = worsening of acute diarrhea.

(Treatment success = GPA score of 1 or 2).

• For toilet trained children only: number of stools per day as well as number of watery stools per day from start of treatment and until end of study treatment.

2.3 Safety Objective(s)

[figure not shown]
To evaluate the safety and tolerability of Racecadotril together with oral rehydration solution (ORS) in infants and children (3 months until 60 months) with acute diarrhea by adverse events, physical examination and vital signs.

3. STUDY DESIGN

3.1 Overall Study Design and Plan-Description

This is a prospective, open-label, multicenter, single-arm study evaluating the efficacy and safety of Racecadotril in infants and children with acute diarrhea in out-patients. The number of subjects to be screened is 50 in order to achieve 40 subjects treated with standard treatment (oral rehydration solution, ORS) plus Racecadotril.

Figure 3-1 Overall Study Design

3.2 Selection of Study Population

Inclusion Criteria

(1) Signed informed consent from one of the parent(s)/legal representative(s).

(2) Subjects, both genders, aged 3 to 60 months.

(3) Subjects with acute diarrhea (defined as the passage of three or more unformed or liquid stools within the last 24 hours and lasting for less than 3 days).

Exclusion Criteria

- (1) Known allergy to Racecadotril or any of its ingredients.
- (2) Subjects suffering from renal or hepatic impairment.
- (3) Subjects with fever > 39 degrees Celsius

(4) Subjects with bloody and/or purulent stools.

(5) Subjects suffering from antibiotic (e.g. amoxicillin)-associated diarrhea, chronic diarrhea or iatrogenic diarrhea.

(6) Subjects with alternating bouts of diarrhea and constipation.

(7) Diarrhea due to exacerbation of chronic gastrointestinal diseases such as irritable bowel syndrome, irritable bowel disease or pancreatic exocrine insufficiency.

(8) Cystic fibrosis or coeliac disease.

(9) Subjects suffering from prolonged or uncontrolled vomiting.

(10) Subjects with rare hereditary problems of fructose intolerance, glucose-galactose malabsorption syndrome or sucrase isomaltase insufficiency.

(11) Subjects having received antibiotic treatment within 2 weeks prior to start of the current diarrhea episode.

(12) Subjects having received antidiarrheal drugs (except pre- or probiotics see Protocol section 7.7.)48 hours prior to Day 1.

(13) Subjects with severe dehydration requiring intravenous fluid or electrolyte replacement or hospitalization treatment.

(14) Subject with a history of angioedema or who had reported angioedema with angiotensin converting enzyme inhibitors (such as captopril, enalapril, lisinopril, perindopril, ramipril)

(15) Subjects with combined diseases or medical situations that would prevent to be enrolled into the study, depending on the judgment of the investigator

(16) Intake of experimental drug within 30 days prior to study start.

(17) Subjects with contraindications to ORS or susceptible to the warnings of ORS.

3.3 Blinding and Treatment Code Information

This is an open-label study; blinding will not be applied.

3.4 Method of Assigning Subjects to Treatment Groups

A maximum number of 48 subjects will be enrolled with a minimum number of 20 subjects in each age group (< 24 months of age and \geq 24 months of age).

Approximately 50 subjects should be screened.

Subjects will be assigned a 5-digit enrollment number. The medication will be identified using 6-digit kit numbers.

The subject numbers will be provided by Clinical Supply Management (Product Development) of Abbott Healthcare Products BV.

3.5 Primary Efficacy Variable

Duration of diarrhea (hours) between the start of treatment until the last watery/diarrheal stool before recovery or the end of study treatment (treatment duration maximal 5 days). Treatment will stop at recovery or after the morning dose of day 6, if not recovered.

Duration of diarrhea is defined as date and time of the evacuation of the final watery/diarrheal stool before recovery derived from the daily diary.

3.6 Secondary Efficacy Variables

- Time until recovery, defined as date and time of the evacuation of the first of two consecutive normal stools or no stool within 12 hours after the first normal stool.
- Number of recovered subjects in total and until each individual treatment day.
- Global Physician Assessment (GPA) at the end of treatment, at the discretion of the investigator:
 - \circ 1 = Complete relief of acute diarrhea,
 - \circ 2 = marked improvement of acute diarrhea,
 - \circ 3 = moderate improvement of acute diarrhea,
 - \circ 4 = slight improvement of acute diarrhea,
 - \circ 5 = no change in acute diarrhea,
 - \circ 6 = worsening of acute diarrhea.

(Treatment success = GPA score of 1 or 2).

• For toilet trained children only: number of stools per day as well as number of watery stools per day from start of treatment and until end of study treatment.

3.7 Safety Variables

Adverse Events

Any untoward medical occurrence in a patient or clinical investigation subject administered a pharmaceutical product and which does not necessarily have a causal relationship with this treatment.

Requirements for collecting, recording and reporting of AEs are described in Protocol Section 9. Each subject is to be evaluated at the termination visit. Should any AE be identified at this visit, the Investigator will continue to follow the subject as described: All AEs occurring during the study are to be followed up in accordance with good medical practice until resolved or judged no longer clinically significant, or if a chronic condition, until fully characterized.

AEs are considered treatment emergent (TE) if they start or worsen at or after the first administration of study drug and before or on the day of last administration of study drug plus a gap period of 1 calendar day.

Vital Signs

Height and weight must be recorded.

Body temperature will be measured in the morning and in the evening with at least 12 hours interval. If the value is >39 degrees Celsius, the measurement has to be repeated within one hour to confirm the value.

Systolic blood pressure (SBP), diastolic blood pressure (DBP) and pulse rate are to be measured in pediatric appropriate setting.

Physical Examination

A physical examination should be performed and any relevant findings are to be recorded on the Medical History form in the CRF (for findings from the past that occurred prior to allocation to treatment), or on the Adverse Event form in the CRF for findings presently occurring.

3.8 Flow Chart of Study Assessments

Table 1:	Flow	Chart	of Study	Assessments
----------	------	-------	----------	-------------

Period	Screening	End of Treatment period	Safety follow-up (phone call, 5-7 days after Visit 2)
Visit	1	2	3
Day	1	6 ²	11-13
Informed consent	X		
Inclusion/exclusion criteria	X		
Demographic data	X		
Medical history including vaccination history	Х		
Physical examination	X	X	

[figure not shown]
Period	Screening	End of Treatment period	Safety follow-up (phone call, 5-7 days after Visit 2)
Vitals signs	Х	Х	
Dispense study drug	Х		
Concomitant medication	Х	Х	X
Compliance check		Х	
Global physician assessment		Х	
Adverse events	Х	Х	X
Collect study drug		Х	
Dispense diary	X^1		
Collect diary		Х	

¹ Subjects' parent(s)/caregiver(s)/legal representative(s) have to fill in their daily diaries continuously.

 2 or within 24 hours (in exceptional justified cases within 48 hours) after recovery if this occurs before day 6

3.9 Interim Analysis

No interim analysis will be performed for protocol Amendment 2, but there will be a dry run of Table, Listing and Figures (TLFs) based on Study Date Tabulation Model (SDTM) and Analysis Data Model (ADaM) datasets to Abbott at a time when 25 randomized subjects complete the study and 40 randomized subjects complete the study. While the subjects enrolled using protocol version date 09 OCT 2017 will be excluded from dry run analysis. Dry run tables will be prepared and reviewed in the blinded fashion.

3.10 Subgroup Analysis

Key efficacy and safety results will be summarized across subgroups defined by age group (< 24 months old and \geq 24 months old).

An additional subgroup analysis which is not included in the protocol will be summarized across subgroups defined by weight group (in infants less than 9 kg, in infants from 9 kg to < 13 kg, in

children from 13 kg to 27 kg, and in children of more than 27 kg). Subgroup analysis by weight groups will be only conducted in the demographics and efficacy.

4. GENERAL STATISTICAL ISSUES

4.1 Continuous Endpoints

Descriptive statistics for quantitative and ordinal variables including number of observation (n), mean, standard deviation (SD), median, minimum (Min) and maximum (Max) will be presented for the raw data as well as change from baseline. The mean will be represented one more decimal than the raw number, and SD as two more decimals than the raw number.

4.2 Categorical Endpoints

For qualitative variables, per category the numbers and frequencies of subjects with non-missing data (n, %) will be the default summary presentation, and if appropriate and present, the number of missing values. Percentages will be presented with 2 decimals. Partial date(s) will be listed as provided in the listings.

For AEs, medical history and concomitant medications, however, the denominator for the percentage calculation will be the number of subjects at risk. A subject will be considered at risk if the subject is in the safety sample and entered the respective study period.

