Subjects will be treated with Racecadotril three times daily according to the body weight dose requirement on an out-patient basis for maximum 5 days. The subjects will be treated with ORS (according to the registered local label and the instruction of the investigator) in addition to Racecadotril. ORS will be prescribed by the investigator and will be taken according to the product label and the instruction of the investigator. The parent(s)/caregiver(s)/legal representative(s) will be instructed to stop study drug treatment when the patient recovered. On each day, the parent(s)/caregiver(s)/legal representative(s) will fill in their diaries, documenting the date and time of each individual stool, the stool consistency of each stool (diarrheal/watery or normal), the amount of ORS, and the study drug intake. After the occurrence of two consecutive normal stools or no stool within 12 hours, the parent(s)/caregiver(s)/legal representative(s) can stop recording of the diary and return to the study site for the end of treatment visit. The date of recovery is the day when the first of two consecutive normal stools were excreted or the day

[figure not shown]
when no stool within 12 hours after the first normal stool was observed. AEs are to be reported on an ongoing basis.

End of treatment (Day 6 or early recovery, Visit 2)

The last dose of study drug will be the morning dose of day 6, if not recovered earlier (last dose will be the morning dose after recovery, ORS can be continued until Visit 2). On the same day, or within 24 hours after recovery (in exceptional cases within 48 hours), the parent(s)/caregiver(s)/legal representative(s) will visit the site for the end of treatment visit of the child. Data on vital signs, AEs, physical examination and concomitant medication will be collected. Subjects will return their diaries and unused medication.

Safety follow-up

A phone call will be performed 5-7 days after the end of the treatment period for the safety follow-up.

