4.4 Sample Size Estimation and Power

In total, 40 subjects will be allocated to receive Racecadotril treatment. Results of a recently finalized study in Russian children showed that all children under Racecadotril treatment recovered within 3 days of drug treatment. A sample size of 40 subjects is sufficient to estimate a two-sided 95% confidence interval with the precision of 3.1 percentage points for a recovery of at least 99% of the subjects after 3 days of Racecadotril treatment. In order to account for drop-outs 48 subjects will be recruited. Recruitment will be stopped once 40 subjects have completed the study.

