6. ANALYSIS OF SUBJECT SAMPLES

The main subject samples of interest are defined as follows.

The all subjects consented sample will consist of all subjects who:

- Gave their informed consent.

The all subjects <allocated to treatment> sample will consist of all subjects who:

- Were in the all subjects consented sample; and
- Were <allocated to treatment>

The safety sample will consist of all subjects who:

- Were in the all subjects allocated to treatment sample; and
- Had at least one dose of study medication administered.

The full analysis (FA) sample will consist of all subjects who:

- Were included in the safety sample; and

- Had data for at least one post-baseline assessment of any efficacy measurement.

The per-protocol (PP) sample will be defined through blind data review and will consist of all subjects who:

- Were included in the FA sample; and
- Did not present any major protocol violation.

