9.2.2 Number of Subjects Recovered

Number and proportion of subjects recovered, in total and until each individual treatment day will be summarized with count and percentage as well as 95% CI as Table 14.2.2 using FA and PP samples.

Subgroup analysis of number and proportion of subjects recovered by age group (< 24 months old and \geq 24 months old) will be also summarized with count and percentage as well as 95% CI as Table 14.2.7 using FA and PP samples.

Subgroup analysis of number and proportion of subjects recovered by weight group (in infants less than 9 kg, in infants from 9 kg to < 13 kg, in children from 13 kg to 27 kg, and in children of more than 27 kg) will be also summarized with count and percentage as well as 95% CI as Table 14.2.12 using FA and PP samples.

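### The proportion recovered and GPA success leave out dosed children with no efficacy data, and the SAP does not say how FA drop-outs without documented recovery count

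*SAP*

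**What the plan says.** - **Samples.** SAP 9 uses the FA and PP samples for all efficacy analyses. Beyond membership of the safety sample, SAP 6 admits a child to FA on one condition: "Had data for at least one post-baseline assessment of any efficacy measurement".
- **Default percentage.** SAP 4.2 states: "For qualitative variables, per category the numbers and frequencies of subjects with non-missing data (n, %) will be the default summary presentation". The same sentence adds the number of missing values, but only where appropriate and present. Adverse events, medical history and concomitant medication are the exceptions; their denominator is subjects at risk in the safety sample.
- **Recovery and GPA.** SAP 9.2.2 reads: "Number and proportion of subjects recovered, in total and until each individual treatment day will be summarized with count and percentage", with a 95% CI. SAP 9.2.3 asks for the same summary of GPA success (score 1 or 2). Neither section sets another denominator or says how a missing outcome is scored.
- **Drop-outs in the time-to-event analysis.** SAP 9.1 places drop-outs with the children who did not recover and censors them.
- **When efficacy data reach the site.** The flow charts in both documents put diary collection and the GPA at Visit 2 only. Protocol 4.1 says of that visit: "Subjects will return their diaries and unused medication". The later telephone call covers adverse events and concomitant medication.
- **Recruitment.** SAP 4.4 states: "In order to account for drop-outs 48 subjects will be recruited", and then: "Recruitment will be stopped once 40 subjects have completed the study".

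**The concern.** A dosed child who never comes back for Visit 2 and returns no diary has no post-baseline efficacy data. That child fails the FA condition and leaves both proportions. A child whose diary is returned but who has no GPA stays in FA and leaves the GPA percentage under the SAP 4.2 default. In either case enrolment continues, up to 48, until 40 children have completed.

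Recovery and GPA success are the only proportions for which the SAP plans confidence intervals, and recovery by day 3 is the quantity that justified the sample size. The trial has one arm, so no control group would share the effect of selective loss. If the children without data tend to be those who did badly, the reported proportions are too high and their intervals sit too far up.

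**Working it through.** **1. The plan's own precision.** SAP 4.4 states: "A sample size of 40 subjects is sufficient to estimate a two-sided 95% confidence interval with the precision of 3.1 percentage points" and continues "for a recovery of at least 99% of the subjects after 3 days of Racecadotril treatment". With n = 40, p = 0.99 and the usual normal approximation:

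1.96 × √(0.99 × 0.01 / 40) = 0.0308, or 3.1 percentage points.

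The stated figure is reproduced. It is the yardstick for the shifts below.

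**2. The room for non-completers.** 48 − 40 = 8, and 8/48 = 16.7%. This allowance covers drop-outs of every kind, not only children without efficacy data.

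**3. Who is in which percentage.**

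| Dosed child | In FA? | Proportion recovered | GPA success |
|---|---|---|---|
| No diary data, no GPA | No | Excluded | Excluded |
| Full diary, no GPA | Yes | Included | Excluded by the SAP 4.2 default |
| Partial diary, dropped out, no recovery recorded | Yes | Not stated in SAP 9.2.2 | Depends on whether a GPA was done |

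For the third row the nearest rule is SAP 9.1, which treats drop-outs as not recovered. That rule is written for the Kaplan-Meier analysis, and SAP 9.2.2 neither repeats nor overrides it.

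**4. Size.** Assume 40 completers who all recovered, plus m dosed children with no efficacy data. As written the result is 40/40 whatever m is. With all dosed children in the denominator and missing counted as not recovered, it is 40/(40 + m). SAP 9.2.2 and 9.2.3 name no interval method, so exact (Clopper-Pearson) limits are used here. For x of n, the lower limit is the 2.5% quantile of Beta(x, n − x + 1) and the upper limit is the 97.5% quantile of Beta(x + 1, n − x). For x = n = 40 the lower limit is 0.025^(1/40) = 0.912 and the upper limit is 1.

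| m | Proportion | Exact 95% CI | Shift from 100% |
|---|---|---|---|
| 0, or any m under the plan as written | 40/40 = 100% | 91.2 to 100 | none |
| 2 | 40/42 = 95.2% | 83.8 to 99.4 | 4.8 points |
| 4 | 40/44 = 90.9% | 78.3 to 97.5 | 9.1 points |
| 8 (ceiling) | 40/48 = 83.3% | 69.8 to 92.5 | 16.7 points |

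Two children already move the estimate by more than 3.1 points. The arithmetic is the same for GPA success if the 40 are all successes and m children have no GPA. It also gives the size of the ambiguity in the third row of step 3: with m partial-diary drop-outs, reading them as missing gives 40/40, and reading them as not recovered gives 40/(40 + m).

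**The case against.** Five points can be made for the plan.

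- **The children are reported.** A reader might infer that they disappear from the report. They do not. Table 14.1.1 summarises premature terminations and assignment to samples, Listing 16.2.3 gives every exclusion with its reason, and SAP 4.2 allows a missing count. This stands. It discloses the loss but leaves the percentage and its interval unchanged.
- **FA is not a completers sample.** A reader might infer that the intervals describe completers only. One efficacy assessment is enough for FA, so an early terminator with a partial diary or a GPA is in. This stands.
- **Many failures should be captured.** Protocol 6 calls for an end-of-treatment visit after premature termination, and diary collection and the GPA belong to that visit. Children withdrawn by the investigator for worsening or hospitalization should therefore usually have data. What is left is mainly families who do not return or who withdraw consent without a visit. A family whose child is well may also stay away, so an upward bias is plausible but not established. This stands, although the provision cannot secure data from a family that does not come back.
- **SAP 9.1 already treats drop-outs as not recovered.** This helps only for children in FA, because FA and PP govern all efficacy analyses, and it is written for Kaplan-Meier.
- **The stakes are limited.** Both variables are secondary and descriptive, with no test or success threshold, and the primary variable is duration of diarrhea. This stands, and it argues for adding a line rather than replacing FA as the main analysis.

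**Conclusion.** The gap is real and narrow. As written, a dosed child without any efficacy data is outside both proportions, an FA child without a GPA is outside the GPA percentage, and the counting of an FA drop-out with a partial diary is not specified for the proportion recovered. If loss is related to failure, the proportions will be too high. Under the assumption of 40 completers who all recovered, 2 such children make the difference between 100% and 95.2%, and 4 make it 90.9%.

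The figure of 83.3% is only a ceiling on the effect. A reader might take it as the expected size, but it needs all 48 children dosed and all 8 non-completers without diary data or a GPA, despite the visit called for in Protocol 6. The documents give no rate for such cases and nothing on whether these children recovered. The case for a change rests on its low cost and on the effect of as few as two children, not on the ceiling.

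**What to change.** In SAP 9.2.2 and 9.2.3, covering Tables 14.2.2 and 14.2.3 and the subgroup versions (14.2.7, 14.2.8, 14.2.12 and 14.2.13):

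1. Keep the FA and PP results.
2. State that an FA drop-out without documented recovery counts as not recovered, in line with SAP 9.1.
3. Always show the number missing, rather than only where appropriate.
4. Beside the FA result, add a line on all dosed children (the safety sample) in which missing recovery counts as not recovered and a missing GPA counts as not a success.

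This takes a few sentences in the SAP and some programming, and no new data. The drawback is that the added figure is less favourable, and a lost child who in fact recovered counts against the drug. The two lines should therefore be read as a range: the FA line takes the missing children to be like those observed, and the all-dosed line takes all of them as failures.

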4.3 Time-to-event Endpoints

The time-to-event endpoint will be analyzed by Kaplan-Meier method and presented as mean, median and 95% confidence interval for median.

4.4 Sample Size Estimation and Power

In total, 40 subjects will be allocated to receive Racecadotril treatment. Results of a recently finalized study in Russian children showed that all children under Racecadotril treatment recovered within 3 days of drug treatment. A sample size of 40 subjects is sufficient to estimate a two-sided 95% confidence interval with the precision of 3.1 percentage points for a recovery of at least 99% of the subjects after 3 days of Racecadotril treatment. In order to account for drop-outs 48 subjects will be recruited. Recruitment will be stopped once 40 subjects have completed the study.

